10.4.2 Safety observation and grade of adverse reaction/event

10.4.2.1 Definition of adverse event and serious adverse event

An adverse event (AE) is any untoward medical occurrence in a participant administered an investigational product and which does not necessarily have a causal relationship with this treatment. An adverse reaction (AR) is all untoward and unintended responses to a medical product related to any dose administered.

A serious adverse event/reaction (SAE) is occurrence of any untoward medical during the whole study period that:

- Result in death.
- life-threatening (an event in which the participant is at risk of death at the time of the event; it does not refer to an event which hypothetically might have caused death if it was more severe).
- Result in persistent or significant disability/incapacity.
- Require hospitalization or prolongation of an existing hospitalization.
- Congenital anomaly/birth defect.

10.4.2.2 Safety observation contents

Adverse events occurred 0-7 day after vaccination.

Adverse events occurred 0-28 day after vaccination.

Serious adverse events within 6 months after vaccination;

Changes of safety laboratory measures (hemoglobin, white blood cell count, total lymphocyte count, platelets, creatinine, alanine transaminase, neutrophil, glutamic oxaloacetic transaminase, total bilirubin, and fasting blood glucose) on day 7.

10.4.2.3 Adverse event classification standard

The adverse events will be graded and evaluated according to the "Guidelines of the Criteria for the Classification of Adverse Events in Clinical Trials for Vaccines" (No.102,2019) of the China Food and Drug Administration. For details, see tables 10-4-1-1, 10-4-1-2, 10-4-1-3.

Table 10-4-1-1 Grading for adverse events at the injection site

Symptoms	Grade 1	Grade 2	Grade 3	Grade 4
Pain	Do not affect or slightly affect physical activity	affect physical activity	Affect daily life	Loss of basic self-care ability or hospitalization
Induration*, swelling (optional)** #	Diameter 2.5~<5 cm or area 6.25~25 cm ² and does not affect or slightly affect daily life	Diameter 5~<10 cm or area 25~<100 cm ² or affect daily life	Diameter ≥ 10 cm or area ≥ 100 cm ² or ulceration or secondary infection or phlebitis or aseptic abscess or wound drainage or seriously affect daily life	Abscess, exfoliative dermatitis, dermal or deep tissue necrosis
Rash*,Redness (optional)** #	Diameter 2.5~<5 cm or area 6.25~25 cm ² and does not affect or slightly affect	Diameter 5~<10 cm or area 25~<100 cm ² or affect daily life	Diameter ≥ 10 cm or area ≥ 100 cm ² or ulceration or secondary infection or phlebitis or aseptic abscess or wound	Abscess, exfoliative dermatitis, dermal or deep tissue necrosis

	daily life		drainage or seriously affect daily life	
Itch	Itching at the vaccination site, relieved by itself or within 48 hours after treatment	Itching at the vaccination site, which does not resolve within 48 hours after treatment	Affect daily life	NA
Cellulitis	NA	Non-injectable treatment is required (e.g. oral antibacterial, antifungal, antiviral therapy)	Intravenous treatment is required (e. G. intravenous antibacterial, antifungal, antiviral therapy)	Sepsis, or tissue necrosis, etc.

Note: *: in addition to directly measuring the diameter for grading and evaluation, the progress of the measurement results should also be recorded.

** the maximum measuring diameter or area should be used.

the evaluation and grading of induration and swelling, rash and redness should be based on the functional level and the actual measurement results, and the indicators with higher classification should be selected.

Table 10-4-1-2 Grading for systemic adverse events.

Systemic symptoms	Grade 1	Grade 2	Grade 3	Grade 4
Diarrhea	Mild or transient, 3 to 4 times a day, abnormal stool, or mild diarrhea last less than 1 week	Moderate or persistent, 5-7 times a day, abnormal stool characteristics, or diarrhea >1 week	>7 times / day, abnormal stool, or hemorrhagic diarrhea, orthostatic hypotension, electrolyte imbalance, need intravenous infusion >2L	Hypotension shock, hospitalization required

Constipation*	Need fecal softener and diet adjustment	Need a laxative.	Stubborn constipation requires manual dredging or use of enema	Toxic megacolon or intestinal obstruction
Dysphagia	Mild discomfort when swallowing	Diet is restricted	Diet and conversation are very limited; you can't eat solid food.	Can't eat liquid food; need parenteral nutrition.
Anorexia	Loss of appetite, but no reduction in food intake	Loss of appetite, reduced food intake, but no significant weight loss.	Loss of appetite and weight loss	Need for intervention (e.g. gastric tube feeding, parenteral nutrition)
Vomiting	1- 2 times/24 hours and does not affect the activity	3- 5 times/24 hours or activity is restricted	>6 times/24 hours or need intravenous rehydration	Hypotension shock requires hospitalization or other means of nutrition
Nausea	Transient (<24 hours) or intermittent and food intake is normal	Continued nausea leads to reduced food intake (24-48 hours)	Persistent nausea results in almost no food intake (> 48 hours) or requires intravenous fluid replacement	Life-threatening (eg hypotension shock)
Non-injection-site muscle pain	Does not affect daily activities	Slightly affect daily activities	Severe muscle pain that seriously affects daily activities	Emergency or hospitalization
Arthritis	Mild pain with inflammation, erythema, or swelling of joints; but does not interfere with function	Moderate pain with inflammation, erythema, or swelling of joints; impairs function but does not affect daily activities	Severe pain with inflammation, erythema, or joint swelling; affecting daily activities	Permanent and / or disabling joint injury

Arthralgia	Mild pain without hindering function	Moderate pain; need analgesics and / or pain that impedes function but does not affect daily activities	Severe pain; need analgesics and / or pain affecting daily activities	Disability pain
Headache	Does not affect daily activities and requires no treatment	Transient, slightly affects daily activities and may require treatment or intervention	Seriously affects daily activities and requires treatment or intervention	Intractable and requires emergency or hospitalization
Syncope	Close to syncope without losing consciousness (pre-syncope)	Loss of consciousness without treatment	Loss of consciousness and needs treatment or hospitalization	NA
Emerging seizures	NA	NA	1-3 times seizures	Prolonged and multiple seizures (eg, continuity seizures) or difficult to control (eg, refractory epilepsy))
Cough	Transient, without treatment	Persistent cough, effective treatment	Paroxysmal cough, uncontrollable treatment	Emergency or hospitalization
Acute bronchospasm	Transient; no treatment needed; FEV1% is 70%-80%	Needs treatment; bronchodilator therapy returns to normal; FEV1% is 50%-70%	Bronchodilator treatment cannot return to normal; FEV1% is 25% -50% or continuous intercostal depression	Cyanosis; FEV1% <25%; or intubation required
Dyspnea	Dyspnea during exercise	Dyspnea during normal activity	Dyspnea at rest	Dyspnea, requiring oxygen therapy, hospitalization or assisted breathing

Non-injection-site itching (no skin lesions)	Slightly itchy without affecting or slightly affecting daily life	Itching affects daily life	Itching makes it impossible to carry on daily life.	NA
Abnormal skin and mucosa	Erythema / itching / color change	Diffuse rash / macular papule / dryness / desquamation	Blister / exudation / desquamation / ulcer	Exfoliative dermatitis involving mucous membrane, or erythema multiforme, or suspected Stevens-Johnsons syndrome
Insomnia*	Mild difficulty in falling asleep, not affecting or slightly affecting daily life	Moderate difficulty in falling asleep, affecting daily life	Serious difficulty in falling asleep, seriously affecting daily life, requiring treatment or hospitalization	NA
Irritate or suppress	Mild irritability or mild suppression	Irritability or lethargy	Inability to soothe or react poorly	NA
Mental disorders (including anxiety, depression, mania, and insanity) should report detailed symptoms	Minor symptoms, no need to visit or behavior does not affect or slightly affect daily life	Has clinical symptoms and needs medical attention or behavior that affects daily life	Need to be hospitalized or unable to support daily life	Have the tendency to harm themselves or others or acute insanity or loss of basic self-care ability
Acute allergic reaction **	Local urticaria (blister) without treatment	Local urticaria requiring treatment or mild angioedema without treatment	Extensive urticaria or angioedema requiring treatment or mild bronchospasm	Anaphylactic shock or life-threatening bronchospasm or throat edema

Fatigue	Does not affect daily activities	Affects normal daily activities	Seriously affects daily activities and cannot work	Emergency or hospitalization
Non-injection-site pain# (Specify the location when reporting)	Minor pain that does not affect or slightly affect daily life	Pain affects daily life	Pain can't carry on daily life	Disability pain, loss of basic self-care ability
Sore throat ***	Transient, without treatment, without affecting daily activities	Sore throat, slightly affecting daily activities	Severe sore throat that seriously affects daily activities and requires medication	

Note: FEV1% refers to forced expiratory volume per second (FEV1) / forced vital capacity (FVC).

* For constipation and insomnia, pay attention to the changes before and after vaccination.

** Refers to type I hypersensitivity.

Refers to pain in non-injection-site other than muscle pain, arthralgia, and headache.

*** Refer to the "Guidelines of the Criteria for the Classification of Adverse Reactions in Preventive Vaccine Clinical Trials" by the China Food and Drug Administration

Among the above systemic adverse events, diarrhea, fatigue, nausea, anorexia, vomiting, sore throat, headache, cough, arthralgia, non-injection-site muscle pain, non-injection-site itching, abnormal skin and mucosa, acute allergic reactions, syncope, acute bronchospasm, and dyspnea are solicited adverse events, and the rest are unsolicited adverse events.

Table 10-4-1-3 Grading for the vital signs

Sign	Grade 1	Grade 2	Grade 3	Grade 4
Fever* (Axillary temperature(°C))	37.3~<38.0	38.0~<38.5	38.5~<39.5	≥39.5,last more than 3 days

Note :* The axillary temperature is usually used in China, and if necessary, it is converted into oral temperature and anal temperature. Generally, oral temperature = axillary temperature + 0.2 ° C; anal temperature = axillary temperature + (0.3 ~ 0.5 ° C). When persistent high fever occurs, the cause of the high fever should be identified as soon as possible.

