8.5 Criteria for pausing or early termination

The investigators will collect daily reports of adverse events after vaccination and report the newly added adverse events to the Data Safety Monitoring Board (DSMB) in time. The DSMB independently analyzes the post-vaccination safety data in each dose group. If an increased risk of participants is found in the course of the study, they send notice to the principal investigator and the sponsor immediately to suspend or terminate the recruiting of participants in clinical trial, during the dose-escalating procedure. If there is a violation of the protocol, GCP or ethical requirements, the sponsor, principal investigator, ethics committee or administrative department shall have the right to suspend or terminate the study, and shall notify other parties and participants and explain the reasons.

Administration of study injections and new enrollments will be paused, if:

- One or more \geq grade 4 adverse reaction or serious adverse event may be associated with vaccination, or
- Occurrence of grade 3 adverse events associated with vaccination in 15% of participants or more (including injection-site reaction, systemic reaction, and change of the safety laboratory measures), or

- Required by sponsor, or
- Required by regulatory authority, or
- Required by institutional review board (IRB).

The study may come to an early termination, if DSMB, sponsor and investigator agree that the risk increased and the risk-benefit for participants is no longer reasonable.

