10.4.2.5 General principles for the grading for other adverse events

The intensity of adverse events not mentioned in the rating table shall be evaluated according to the following criteria.

Grade 1	Grade 2	Grade 3	Grade 4	Grade 5
Mild: short-term (< 48h) or mild discomfort, does not affect activity, no need for treatment	Moderate: mild or moderate limitation of activity, which may require medical treatment, no or only mild treatment	Severe: obviously limited activity, need to see a doctor and receive treatment, may need to be hospitalized	Critical: may be life-threatening, activities are severely restricted, and need monitoring and treatment	Death

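### The fever scale gives no grade to a temperature of 39.5 °C or more lasting 3 days or less, so such a fever adds to neither grade-based pause trigger

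*Protocol*

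**What the plan says.** Section 10.4.2.3 of the protocol grades adverse events by a national guideline and sends the reader to its own tables: "For details, see tables 10-4-1-1, 10-4-1-2, 10-4-1-3". The fever row of Table 10-4-1-3 uses axillary temperature. Grade 1 runs from 37.3 to below 38.0 °C, grade 2 from 38.0 to below 38.5 °C, and grade 3 from 38.5 to below 39.5 °C. None of these three has a duration condition. Grade 4 is "≥39.5,last more than 3 days". The footnote deals with conversion to oral and anal temperature and with finding the cause of a persistent high fever. It assigns no grade.

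Section 10.4.2.5 supplies a general scale with this scope: "The intensity of adverse events not mentioned in the rating table shall be evaluated according to the following criteria".

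Section 10.4.6 makes the severity grade part of the record of each adverse event. Section 8.5 builds two pause triggers on grade. One is met by one or more reactions at or above the stated level: "grade 4 adverse reaction or serious adverse event may be associated with vaccination". The other is "Occurrence of grade 3 adverse events associated with vaccination in 15% of participants or more".

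In Table 10-4-1-2, vomiting is grade 2 at "3- 5 times/24 hours or activity is restricted" and grade 3 at ">6 times/24 hours or need intravenous rehydration".

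**The concern.** A severity scale should give every observation one grade and should not lose a case as it gets worse. Here grade 3 stops at a temperature limit, and the next grade adds a second condition, duration. Any fever that meets the temperature limit but not the duration falls between them.

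Two uses of the grade are at stake. One is the description of reactions by severity, where a short, very high fever would have no cell. The other is the pair of grade-based pause triggers, where it would add nothing to either count. There is a timing effect too. Even a fever that ends up as grade 4 has no grade until it has lasted more than 3 days, while adverse events are collected daily and dose groups are enrolled one after another. The situation is not far-fetched: Section 13.3.1 names fever among the common reactions to vaccination.

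**Working it through.** There is no stated sample size or power figure to reproduce. The check applies the table literally and then carries the result into the pause rule.

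**Step 1. The fever row as printed.** Inputs are the four cells of Table 10-4-1-3, with grade 4 read as temperature of at least 39.5 °C and duration of more than 3 days.

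| Temperature (°C) | 1 day | 2 days | 3 days | 3.5 days | 4 days |
|---|---|---|---|---|---|
| 38.5 | 3 | 3 | 3 | 3 | 3 |
| 39.4 | 3 | 3 | 3 | 3 | 3 |
| 39.5 | none | none | none | 4 | 4 |
| 40.0 | none | none | none | 4 | 4 |
| 41.0 | none | none | none | 4 | 4 |

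For one day, 39.4 °C is grade 3 and 40.0 °C has no grade.

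**Step 2. Does other text close the gap?** The general scale in Section 10.4.2.5 is limited to events outside the rating tables, and fever is inside one. The footnote to the fever row assigns no grade. If the comma in the grade 4 cell is read as *or*, every fever of 39.5 °C or more becomes grade 4. But so does every fever lasting more than 3 days, even one of 37.4 °C, which then sits in grade 1 and grade 4 at once. Elsewhere in these tables alternatives are written with an explicit *or*.

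**Step 3. The pause rule.** Inputs are the 15% in Section 8.5 and 36 participants per group, 108 in all, in Sections 8.1 and 8.4. Section 8.5 does not say whether the percentage is per group, so both denominators are shown.

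- Per group: 0.15 × 36 = 5.4, so 6 participants are needed (6/36 = 16.7%; 5/36 = 13.9% is not enough).
- Overall: 0.15 × 108 = 16.2, so 17 are needed (17/108 = 15.7%; 16/108 = 14.8% is not enough).

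One related, non-serious fever of 39.5 °C or more lasting 3 days or less then counts as follows:

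- as printed: 0 toward either trigger;
- if the sponsor's reconciled table made it grade 3: 1 of the 6 (or 17) needed;
- if it made it grade 4: the trigger is met by that single event.

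**Step 4. Illustration with assumed rates.** The document gives no expected rate of such fevers, so 2%, 5% and 10% of a group of 36 are assumptions, as is a 5% rate *o* of other related grade 3 events, independent of the fevers. With fever rate *p*, the chance of at least one such fever is 1 − (1 − *p*)^36. The chance of at least 6 grade 3 participants is the upper binomial tail for n = 36 with probability 1 − (1 − *o*)(1 − *p*).

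| Assumed rate of short fever ≥39.5 °C | P(at least 1 of 36): pause if grade 4 | P(at least 6 of 36) if grade 3 | P(at least 6 of 36) with these fevers ungraded |
|---|---|---|---|
| 2% | 0.52 | 0.035 | 0.008 |
| 5% | 0.84 | 0.13 | 0.008 |
| 10% | 0.98 | 0.43 | 0.008 |

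**Step 5. Vomiting.** By count, grade 2 ends at 5 and grade 3 begins above 6. Six episodes are still graded if activity is restricted or intravenous rehydration is needed. Six episodes with neither have no grade.

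**The case against.** The best case against the point is that little depends on it. Section 8.5 also allows a pause for a possibly related serious adverse event of any grade, which a fever leading to hospital admission would be, and at the request of the sponsor, regulator or IRB. The DSMB receives adverse events as they occur and can call for suspension. Section 8.1 has safety data evaluated daily and recruiting stopped if a safety problem appears, and participants with fever must report to a designated hospital. All of this stands. A reader might infer that the trial could not pause for a short, very high fever; the document does not support that. The gap is confined to the two grade-based triggers and the severity record.

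A reader might also infer that the primary result is compromised. It is not: the primary endpoint in Section 8.2.1 is occurrence of adverse reactions within 7 days, without regard to grade, and an ungraded related fever still counts.

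It can be said that a fever reaching 39.8 °C passes through the grade 3 range and might be recorded there. That may happen in practice, but the table does not say which reading sets the grade, and the same argument would place it in grades 1 and 2 as well.

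The cited guideline is not at hand, so whether the cell is a transcription or translation slip cannot be settled. That limits any statement about the cause, not the observation that the table needs reconciling.

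Finally, the creatinine row might look like a similar fault, with gaps between 1.5 and 1.6 and between 3.0 and 3.1 times the upper limit of normal. Those limits adjoin if multiples are taken to one decimal, a style used elsewhere in the laboratory tables, so no point is made of them.

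**Conclusion.** The point holds as a defect of the grading table. On its natural reading, a fever of 39.5 °C or more lasting 3 days or less has no grade, while a milder one of the same length is grade 3. It is unscored rather than scored lower. The consequence is limited to severity tabulation and the two grade-based pause triggers.

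The size depends on how many such fevers occur and on the grade they are meant to have. The document fixes neither. Each one is worth nothing as printed, one participant toward 6 of 36 or 17 of 108 under grade 3, and a pause on its own under grade 4. The probabilities above rest on assumed rates and a per-group denominator; they show how far the answer can move and are not a forecast. A reader could construct counts that land on opposite sides of 15% (for instance 3/36 = 8.3% against 6/36 = 16.7%), but no rate in the protocol makes that pattern likely. With 108 as the denominator the same counts are 2.8% and 5.6%, both below the threshold.

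The conclusion assumes that the comma in the grade 4 cell joins two conditions. If it does not, the row overlaps lower down and still needs correction. The vomiting gap is real but narrow.

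**What to change.** The sponsor should reconcile the grade 3 and grade 4 fever cells of Table 10-4-1-3, checking them against the guideline cited in Section 10.4.2.3. Every combination of axillary temperature from 37.3 °C and duration should map to exactly one grade, and the grade should never fall as temperature rises. Because the grade feeds a pause criterion, which grade a short fever of 39.5 °C or more receives is for the sponsor's medical lead to decide; none is proposed here. The vomiting row of Table 10-4-1-2 should be reconciled in the same edit for exactly 6 episodes in 24 hours without activity restriction or intravenous rehydration. A matching eCRF check should reject any fever record that has no grade or more than one.

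The cost is a table edit and one programmed check. The downside is that reported rates of severe fever may be slightly higher and a pause may be triggered sooner.

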10.4.2.4 Grading for laboratory testing index

Table 10-4-1-4 Grading for blood biochemical indicators

Index	Grade 1	Grade 2	Grade 3	Grade 4
Liver function (ALT, AST increase)	1.25~<2.5 ×ULN	2.5~<5.0×ULN	5.0~<10×ULN	≥10×ULN
Increase of total bilirubin (mg/dL; μmol/L)	1.1~<1.6×ULN	1.6~<2.6×ULN	2.6~5.0×ULN	≥5.0×ULN
Hyperglycemia (fasting) (Glu,mmol/L)	6.11~<6.95	6.95~<13.89	13.89~<27.75	≥27.75
Hypoglycemia (Glu, mmol/L)	3.05~<3.55	2.22~<3.05	1.67~<2.22	<1.67
Creatinine (μmol/L)	1.1~1.5×ULN	1.6~3.0×ULN	3.1~6×ULN	>6×ULN

Note: ULN means the upper limit of the normal value range

Table 10-4-1-5 Grading for blood routine indicators

Index	Grade 1	Grade 2	Grade 3	Grade 4
White blood cell increase(WBC,10⁹/L)	11~<13	13~<15	15~<30	≥30
White blood cell decrease (WBC, 10⁹/L)	2.000~2.499	1.500~1.999	1.000~1.499	<1.000
Lymphocyte decrease (LY, 10⁹/L)	0.75~1.00	0.5~0.749	0.25~0.49	<0.25

Neutrophils decrease (ANC, 10⁹/L)	0.800~1.000	0.600~0.799	0.400~0.599	<0.400
Platelets decrease (PLT, 10⁹/L)	125~140	100~124	25~99	<25
Low hemoglobin (g/dL)				
Male	10.0~10.9	9.0~<10.0	7.0~<9.0	<7.0
Female	9.5~10.4	8.5~<9.5	6.5~<8.5	<6.5

Note: ULN means the upper limit of the normal value range.

10.4.2.5 General principles for the grading for other adverse events

The intensity of adverse events not mentioned in the rating table shall be evaluated according to the following criteria.

Grade 1	Grade 2	Grade 3	Grade 4	Grade 5
Mild: short-term (< 48h) or mild discomfort, does not affect activity, no need for treatment	Moderate: mild or moderate limitation of activity, which may require medical treatment, no or only mild treatment	Severe: obviously limited activity, need to see a doctor and receive treatment, may need to be hospitalized	Critical: may be life-threatening, activities are severely restricted, and need monitoring and treatment	Death

10.4.3 Outcome of AE

The outcomes of adverse reaction / event include: (1) Recovery; (2) Not yet recovered; (3) Recovered but sequelae; (4) Death; (5) Loss of visit

